Initially, potential subjects from HERON, Pioneers, and KUH outpatient HF clinics will be interviewed by phone for potential recruitment in the study. Two nurse practitioners and a cardiologist on our research team work in the outpatient HF clinics and will refer patients to us. Patients will be required to speak English, and the informed consent and patient information will be written at the 8th grade level. We will collaborate with our Human Subject Protection Program to ensure our consent form complies with the US Department of Health and Human Services (HHS) federal guidelines and obtain informed consent from eligible patients (Appendix 10). Patients that have consented will be provided a 1-week supply of placebo ubiquinol pills (instructed to take 2 pills/day) and placebo D-ribose powder (instructed to take 3 scoops/day) as a pre-randomization run-in period to evaluate compliance to the supplements. Patients will be scheduled for an appointment at the CTSU in 1 week following the run-in period. Patients that demonstrate an 80% compliance rate of ubiquinol intake (as evidenced by pill count) and an 80% compliance rate of D-ribose powder intake (as evidenced by weight of the containers) will be eligible to be randomized into a group assignment. The enrolled patients with 80% compliance will then be randomized into four groups (69 subjects in each group) to receive ubiquinol (600 mg daily), D-ribose (15 g daily), ubiquinol plus D-ribose, or placebo for a period lasting 12 weeks. Both the ubiquinol and the D-ribose supplements used in the study will have a certificate of analysis from the manufacturer (Appendix 9). The Project Director will receive the identified list of recruited subjects from the Principal Investigator (PI) and will randomly assign subjects to one of the groups using a list created by a computer-based random number generator. All supplements and the placebo will be indistinguishable in packaging and will be distributed by the Project Director independent of the PI so that the allocation of subjects to a treatment or placebo group will be concealed from both subjects and research personnel.

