All subjects will complete the demographic form at baseline. The KCCQ (Appendix 2) and Vigor scale from the Profile of Mood States (POMS) will be completed in CTSU visits at baseline and 12 weeks (Appendix 3) along with the subject's height and weight. The patient will be escorted to a private room and asked to remove clothing above the waist. A disposable gown will be provided and the patient will lay supine on the bed while an echocardiogram is completed. Approximately 0.5 ml of blood will be collected via finger stick to measure lactate, ATP, and BNP. Next, the subject will complete a 6MWT (Appendix 4, Borg scale). Approximately 2 hours will be required for each subject's visit to the CTSU. Follow-up calls will occur at 3, 6, and 9 weeks during the trial.

Potential Problem and Alternative Solutions. Serum CoQ10 and D-ribose values in some of the treatment patients might be below threshold levels at 6 weeks, possibly due to subject non-adherence. If this occurs, the Project Director, who is not blinded to the list of placebo and treatment subjects, will call and ask if there are any problems with consuming the ubiquinol and/or D-ribose. The Project Director and Research Associate will conduct a phone follow-up interview at 3, 6, and 9 weeks during the trial using a structured interview. Questions asked will relate to any side effects and compliance history in taking their capsules or powder.

Various cardiovascular risk factors will be recorded such as tobacco usage, diabetes mellitus, hypercholesterolemia, hypertension, and family history of cardiovascular disease. Smoking status will be recorded as either smoker or non-smoker. Patients who use tobacco will be given contact information for a tobacco/smoking cessation program. Diabetes mellitus will be determined by a history of the disease or use of medication for diabetes. Hypercholesterolemia will be defined as a fasting total serum cholesterol level ≥ 4.9 mmol/l or use of medication. Hypertension will be defined as either systolic or diastolic blood pressure $\geq 140/90$ mmHg or use of hypertensive medications.

C.3. Aims and Hypotheses.

AIM #1: *To determine the effects of oral ubiquinol, D-ribose, or a combination of the two administered during 12 weeks on symptoms accompanying low bioenergetics in patients with HFpEF.*

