The University's Institutional Review Board (IRB) will review and approve this study prior to implementation. Recruitment of subjects (patients with diastolic heart failure, or HFpEF) will be conducted by the Principal Investigator (PI) and research staff including Project Director and Research Associate in Kansas City, Kansas, and through the University of Kansas Hospital. Patients with HFpEF will be asked for permission to be contacted, have the study explained, be invited to participate, and will be provided written informed consent. The potential subjects will be informed that the purpose of the study is to examine the effects of oral ubiquinol, D-ribose, or a combination of the two in treating patients with HFpEF. Consent forms and Health Insurance Portability and Accountability Act (HIPAA) disclosure information per IRB will be given to all subjects and their signatures will be obtained and witnessed, if they agree to participate. The consent forms will include a description of the study, nature of the data collection, the potential benefits and adverse reactions anticipated, and the methods used to ensure confidentiality. The standard care of subjects will not be changed, withdrawn, or reduced for any subject in this study. The research team personnel will abide by all tenets of the University confidentiality policies as well as the Privacy Protection for Research Subjects. All research staff will keep their required Human Subjects Protection and HIPAA certification current.

The University of Kansas Medical Center (KUMC) *Tutorial for Human Subjects' Protection* program examines the historical context for human subjects' protection; the foundational principles that govern the ethical conduct of research; policies and practices that promote the welfare of research volunteers; and the collective responsibilities shared by the institution, faculty, and staff. The KUMC *Tutorial for HIPAA* provides legal and ethical information about protected healthcare information. Research regulations are reviewed by the KUMC HIPAA Compliance Program Office. Training on HIPAA regulations will be conducted for project staff by [name], PhD, who directs HIPAA Compliance at the University.

1. Risks to Human Subjects.

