2.1. Recruitment and Informed Consent. All recruitment, consent, and data forms for the study proposal will be submitted to the University's IRB prior to subject enrollment. Informed consent will be obtained by a trained research team member (either the Project Director or Research Associate) who has completed an approved Human Subjects' protection certification program. Consent includes the standard elements: Study description, potential risks, benefits, and options for non-participation. Prior to proceeding with enrollment, personnel will ask the subjects to confirm that they know what components of the study involve. Consent will be documented as a signed form and will be kept in a locked file cabinet in a locked study office at the CTSU. In this study, recruitment materials will target subjects with HFpEF. Invitation letters and advertisement flyers about the study will be sent by the research team at the University of Kansas Medical Center (KUMC). Using this process, the PI will not have any knowledge or contact with a potential study participant without permission. A list of potential subjects who enrolled in the Frontier Participant Registry will also be obtained upon approval by HERON. In addition, the Pioneers Recruitment Registry (Pioneers) will be used to assist with recruiting Black/AA, Hispanic/Latino, American Indian/Alaska Native, Asian, and Native Hawaiian/Pacific Islander subjects. The Pioneers Registry has an agreement with Swope Health Services to recruit minorities for studies. The two nurse practitioners and [name] at MidAmerica Cardiology will also provide potential HFpEF patients for the research team to approach for participation in the study. Following permission, the Project Director or Research Associate will contact the potential participant and use a scripted approach to discuss the consent for the study and to answer all the participant's questions. If individuals agree to participate in the study, they

must verbally indicate that they understand the purpose of the study and their rights as participants. The returned, signed consent forms will be considered indicative of informed consent for this study. Due to time commitment to the study, subjects will be compensated for their time at each visit to the CTSU. A bonus incentive will be paid to subjects that complete two CTSU visits.

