This includes the University of Kansas Hospital, Institute for Community Engagement and Frontiers: Heartland Institute of Clinical and Translational Research (HERON), Pioneers Community Registry, all of which have HF patients signed up to volunteer to participate in HF research. In addition, the Pioneers group has an agreement with Swope Health Services which is an inner city clinic that is over 60% Black/AA, 30% Hispanic/Latino, and 10% other races/ethnicity. Thus, we will screen at least 900 patients with HF across the 3-year study timeline. Of these 900 from various sources, we expect 600 patients will be eligible to enroll. Based on [name] recent HF trial, enrolling patients (N=276) from various registries and lists should be feasible.

7. We Proposed Several Research Plans to Overcome Any Problems.

Potential participants will be identified prospectively by the Mid-America Cardiology nurse study coordinator who reviews electronic medical records for 40 cardiologists. During recruitment, we will explain the various required time periods for testing and the different potential groups to which patients might be assigned. Our Project Director will assist us in recruiting subjects. Further, several previous study participants from [name] grant have volunteered to become involved in this study.

8. Investigators Involvement in Human Subjects Training.

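### The Project Director assigns from the random list, is unblinded, and also recruits and may consent patients; the plan describes no step hiding upcoming assignments from this role, so the concealment it claims is not secured.

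*Combined protocol and SAP*

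**What the plan says.** **Assignment (C.2, Study Design and Materials).** The PI passes on the names of recruited patients, and the Project Director "will randomly assign subjects to one of the groups using a list created by a computer-based random number generator". Supplies are "distributed by the Project Director independent of the PI so that the allocation of subjects to a treatment or placebo group will be concealed"; the text extends this to participants and research staff alike.

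**Blinding status (C.2, Potential Problem and Alternative Solutions).** The text refers to "the Project Director, who is not blinded to the list of placebo and treatment subjects".

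**Recruitment (Participation of Human Subjects, opening paragraph).** Recruitment "will be conducted by the Principal Investigator (PI) and research staff including Project Director and Research Associate". Section 7 of that part adds: "Our Project Director will assist us in recruiting subjects".

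**Contact and consent (2.1, Recruitment and Informed Consent).** "Informed consent will be obtained by a trained research team member (either the Project Director or Research Associate"). The same two roles make contact with candidates and discuss consent from a script.

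**Between consent and assignment (C.2).** Patients take placebo capsules and powder for one week. They must reach 80% compliance on each, by pill count and container weight, before they can be randomized. The plan does not name who makes that determination.

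**The concern.** Randomization protects against selection bias only if the people who influence entry do not know the next assignment. C.2 separates the list from the PI. It does not separate it from the other role that approaches and consents patients. The Project Director is named among the research staff, so the statement that allocation is hidden from research personnel does not hold for this role as written.

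If someone who could see the next entry also influenced who was approached or when a visit was booked, the arms could differ in prognosis at baseline. Later blinding of patients and assessors would not repair that. The main analysis in C.5 compares mean KCCQ change by t-test, and adjustment for measured covariates could not remove selection on unmeasured judgement. There is room for choice: section 6 of the human-subjects part expects 600 eligible patients for 276 places.

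**Working it through.** **1. Roles side by side**

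| Task | Role named | Where |
|---|---|---|
| Assigns from the list | Project Director | C.2 |
| Distributes supplies | Project Director | C.2 |
| Unblinded | Project Director | C.2, Potential Problem |
| Recruits | PI, Project Director, Research Associate | Human Subjects opening; section 7 |
| Contacts candidates, discusses consent | Project Director or Research Associate | 2.1 |
| Obtains consent | Project Director or Research Associate | 2.1 |
| Judges run-in compliance | not named | C.2 |

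The documents describe no sealed envelopes, no list held centrally or by the pharmacy, and no release of one assignment at a time after eligibility is final.

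**2. The plan's own figure.** C.5 gives 62 per group, a 10-point difference, SD 12.3, a two-sided test, and 0.05 with Bonferroni for four comparisons (0.05/4 = 0.0125). Power is 97.9% by the normal approximation and 97.6% by the noncentral t, against the stated 98%. Attrition: 62/(1 − 0.10) = 68.9, so 69 per group and 4 × 69 = 276. The sample size reproduces, and the point does not depend on it.

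**3. Illustration with no true effect.** From the documents: n = 62 per arm, SD 12.3, alpha 0.0125. Assumed, with no source in the documents:
- q is the share of candidates passed over: the least promising for active slots, the most promising for placebo slots.
- r is the correlation of that judgement with KCCQ change.

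The mean shift in the judgement after truncation is k = φ(z_q)/(1 − q). At q = 0.20, k = 0.2800/0.80 = 0.350. At q = 0.10, k = 0.1755/0.90 = 0.195.

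The two arms shift in opposite directions, so the false standardized difference is d = 2 × k × r, and in points d × 12.3. The error rate is the two-sided rejection probability of a noncentral t with 122 degrees of freedom and noncentrality d × √(62/2).

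| q | Patients affected | r | d | Points | Error rate |
|---|---|---|---|---|---|
| 0.20 | all | 0.2 | 0.140 | 1.7 | 4.3% |
| 0.20 | all | 0.3 | 0.210 | 2.6 | 9.0% |
| 0.20 | all | 0.4 | 0.280 | 3.4 | 16.9% |
| 0.20 | half | 0.2 | 0.070 | 0.9 | 1.9% |
| 0.20 | half | 0.3 | 0.105 | 1.3 | 2.8% |
| 0.20 | half | 0.4 | 0.140 | 1.7 | 4.3% |
| 0.10 | all | 0.2 | 0.078 | 1.0 | 2.1% |
| 0.10 | all | 0.3 | 0.117 | 1.4 | 3.3% |
| 0.10 | all | 0.4 | 0.156 | 1.9 | 5.1% |

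The reference error rate is 1.25%. In the half rows the false difference is halved. The table applies to the three placebo comparisons. Ubiquinol versus the combination is unaffected in this scenario, because both arms are active and shift alike.

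**The case against.** A reader might infer that the Project Director knows the next assignment, or even that entry will be steered. The documents support neither. The unblinding statement concerns the list of placebo and treatment subjects and does not expressly mention unfilled slots. Section 1.1 of the human-subjects part describes a randomly generated number from a statistical package, which could mean one number drawn per patient. What stands is that C.2 has this role assign from a list and describes nothing that hides its later entries.

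A reader might also infer that the Project Director decides how loosely worded exclusions are read, such as those on valvular disease or cognitive impairment, or chooses the order in which names meet the list. No text gives the role either power. A nurse study coordinator identifies candidates from medical records, clinicians refer patients, and the PI supplies the list of recruited subjects. These two routes should not be counted.

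Two features dilute the risk. Consent comes before a one-week run-in with a measured 80% rule, so the next slot when a patient is approached need not be the slot that patient fills. The Research Associate also shares contact and consent, so some patients may never meet the list holder before assignment. Both objections stand as reductions. Neither removes the risk, because whom to approach and when to book remain open and nothing limits the Project Director's share.

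The size of the effect rests on assumed values, and the case where all patients are affected is the upper end.

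**Conclusion.** The point holds as a risk that the plan leaves open. One unblinded role assigns from the list, recruits, and may take consent, and the only stated protection is independence from the PI. The claim of concealment from research personnel is therefore not secured. It is not a demonstrated breach.

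Under the assumed 20% steering and correlations of 0.2 to 0.4, the false KCCQ difference is 1.7 to 3.4 points with error of about 4% to 17% per active-versus-placebo comparison if all patients are affected, and 0.9 to 1.7 points with about 2% to 4% if half are. The case for change rests on the role overlap and not on these numbers. It should be fixed, because selection at entry cannot be undone in the analysis.

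**What to change.** Remove the Project Director from recruitment, consent, and run-in and eligibility decisions. Give these to the Research Associate, whom 2.1 already names for contact and consent. State that the Research Associate has no access to the list; the plan is silent on this. Assign patients strictly in the order in which their eligibility is recorded as final. The cost is a heavier workload for the Research Associate. Sample size, alpha and power do not change.

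Alternatively, if the pharmacy agrees, it holds the list and releases the next assignment only after eligibility is recorded as final. Appendix 9 describes the pharmacy as preparing, packaging and labelling placebo and providing bottle labels with a participant-number field, so holding the list would be a small new service, with a brief wait at each assignment.

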
come to the Clinical and Translational Science Unit (CTSU), a newly renovated facility with private examination rooms, pharmaceutical rooms, and storage area (for echocardiogram, i-stat instrument, etc.), and computer access to the Velos eResearch for patient data. The facility has plentiful free/close parking.

C.2. Study Design and Materials. Both HFpEF patients and stakeholders had a meaningful influence on the study design. We held focus groups, made individual phone calls, and had in-person meetings with patients with HFpEF. Our Stakeholder Advisory Panel (SAP) consists of diverse individuals including patients, caregivers, clinicians, and hospital administrators (Appendix 1) who have met three times. The patients and caregivers were particularly interested in whether ubiquinol, D-ribose, or both could enhance health status, decrease symptoms, and improve energy levels. We invited 30 HFpEF patients and their caregivers to provide input and feedback regarding the development of our research hypotheses and methods. We found their opinions extremely valuable in designing this patient-centered study.

Study Design, Including Screening, Enrollment, Visits, and Phone Follow-up (Figure 3).

Based on the power analyses (see C.5.), this randomized, double-blind, controlled trial will have a total sample size of (N) = 276. All participants will receive usual care for HFpEF. Efforts will be made to recruit 50% females, which is the actual proportion of HFpEF patients in Kansas City.

N1 = 69 subjects: Control, receive no ubiquinol and no D-ribose; placebo capsules & powder per day.
N2 = 69 subjects: Ubiquinol group, receive 600 mg of ubiquinol/day, D-ribose placebo powder per day.
N3 = 69 subjects: D-ribose group, receive 15 g of D-ribose/day, placebo capsules for ubiquinol per day.
N4 = 69 subjects: Ubiquinol + D-ribose group, receive 600 mg ubiquinol and 15 g D-ribose per day.

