Hypothesis #1. Ubiquinol (600 mg daily), D-ribose (15 g daily), or a combination of the two will enhance the health status of patients with HFpEF as measured by the Kansas City Cardiomyopathy Questionnaire (KCCQ).

Primary outcomes of the study are patient-centered, thus the measurement of health status will be a priority. Bioenergetics has both biological and behavioral components. The biological component (i.e., improved heart function) and its measurement will be discussed below (Aim #2). In this section we will discuss the behavioral component that relates to patients' perceptions of their health status (i.e., symptoms) and the impact of their health status on daily functioning (e.g., hobbies, work, and energy).

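### The trial is labelled double-blind, but an unblinded Project Director contacts participants, one call depends on the arm, and the placebo powder is not specified to match D-ribose in taste or odor

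*Combined protocol and SAP*

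**What the plan says.** Section C.2 describes "this randomized, double-blind, controlled trial". It adds that "allocation of subjects to a treatment or placebo group will be concealed from both subjects and research personnel". In the same section, the Project Director assigns subjects from the random list and distributes the products.

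The C.2 paragraph on potential problems then describes that role's contact with participants:

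- "The Project Director and Research Associate will conduct a phone follow-up interview at 3, 6, and 9 weeks during the trial". The interviews cover side effects and compliance. Section 2 (Adequacy of Risk Protection) makes them structured, under 5 minutes and neutral in tone.
- "Serum CoQ10 and D-ribose values in some of the treatment patients might be below threshold levels at 6 weeks". In that event, "the Project Director, who is not blinded to the list of placebo and treatment subjects, will call and ask if there are any problems" with taking the products. No matching contact is described for placebo patients.

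C.2 lists the blood work as follows: "Approximately 0.5 ml of blood will be collected via finger stick to measure lactate, ATP, and BNP". No serum CoQ10 or D-ribose sample is described.

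Appendix 9 describes D-ribose powder as having a fruity, sweet odor and a slightly sweet taste. It makes the placebo powder from microcrystalline cellulose alone and matches the two powders on color, consistency and container. For the capsules, the same appendix also matches odor. A general sentence promises placebos that match both products but lists no attributes.

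Before randomization, every consented patient takes placebo capsules and "placebo D-ribose powder (instructed to take 3 scoops/day) as a pre-randomization run-in period".

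Section C.3 states: "Primary outcomes of the study are patient-centered". KCCQ and Vigor are completed at the baseline and week-12 visits. If large print is not enough, staff may read out and fill in both forms; their role and blinding are not stated. The monitoring plan (1.2) names one more unblinded person, the cardiologist who determines adverse events.

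**The concern.** An unblinded person who holds the list and dispenses is ordinary. It is avoidable for the same person to interview participants, and it conflicts with the statement that allocation is concealed from research personnel. The call for low serum values is the sharper problem. A neutral script does not help when receiving the call is itself informative about the arm.

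The powder gap is specific. Odor was considered for the capsules but not for the powder, which is the product described as having one. After a week on placebo powder, only patients assigned D-ribose change to a different substance.

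KCCQ and Vigor rest on patient report. If patients recognize D-ribose, expectation could be mixed with drug effect in three of the four planned comparisons: D-ribose versus placebo, combination versus placebo, and ubiquinol versus combination.

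**Working it through.** **1. Texts side by side**

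| Topic | One place | Another place |
|---|---|---|
| Who is blinded | C.2: allocation concealed from subjects and research personnel | C.2, potential problems: Project Director not blinded; monitoring plan 1.2: a cardiologist unblinded |
| Who is called | Weeks 3, 6 and 9: scheduled for all participants | Low-serum call: treatment patients only |
| Trigger for that call | 6-week serum CoQ10 and D-ribose | Blood described only for lactate, ATP and BNP |
| Matching | Capsules: odor, texture, hardness, packaging | Powder: color, consistency, container |

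The first row is a contradiction. The second is a rule that depends on the arm. The third means the trigger has no described measurement. The fourth is a gap in the specification.

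**2. Which comparisons the powder touches**

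The control and ubiquinol arms take placebo powder; the D-ribose and combination arms take D-ribose powder. Three of the four planned comparisons set one powder against the other. Ubiquinol versus placebo has the same powder on both sides.

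**3. The plan's own power figure**

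Inputs from C.5: 62 per group, a difference of 10 points, SD 12.3, two-sided alpha 0.05/4 = 0.0125.

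- d = 10/12.3 = 0.813.
- Noncentrality = d × √(n/2) = 0.813 × √31 = 4.53, with 122 degrees of freedom and critical t = 2.535.
- Power is 97.6% (noncentral t) or 97.9% (normal approximation). The plan says at least 98%, so the figure reproduces to within rounding.
- The smallest observed difference that reaches significance is 2.535 × 12.3 × √(2/62) = 5.6 points.

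**4. Illustration of powder recognition**

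The documents give no size for any reporting bias, so the shift is assumed: no drug effect, and a mean KCCQ shift in the D-ribose-powder arms of 1.5 points (for example, half the patients recognize the powder and shift by 3) to 3 points (all do). The test is the same, with d = shift/SD.

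Two SDs are used. The first is the plan's 12.3. The second is the pooled baseline SD for the clinical summary score in Table 1: √((21.9² + 28.3²)/2) = 25.3. It equals the SD of change only if the correlation between baseline and week 12 is 0.5, which is an assumption.

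| Mean shift | SD 12.3: d, noncentrality, P(significant) | SD 25.3: d, noncentrality, P(significant) |
|---|---|---|
| 0 | 0, 0, 1.25% | 0, 0, 1.25% |
| 1.5 | 0.122, 0.68, 3.5% | 0.059, 0.33, 1.7% |
| 3 | 0.244, 1.36, 12.4% | 0.119, 0.66, 3.3% |

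These are rates per affected comparison. Under the same assumptions, ubiquinol versus placebo stays at 1.25%. The table models powder recognition only; nothing in the documents allows a figure for the calls.

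**5. Call load**

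276 × 3 = 828 calls. At under 5 minutes each: 828 × 5 = 4,140 minutes, so under 69 hours over the whole trial.

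**The case against.** The strongest reply is that no path from the Project Director to the outcome is shown. KCCQ is self-administered, and both questionnaires are completed at visits, not on calls. No passage has the Project Director collect either. The routine calls go to all arms and are brief and scripted. This stands, and the routine calls are a limited route. A reader might infer that the unblinded caller gathers the primary outcome, but the documents do not say so.

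The low-serum call is a contingency without a described sample, so it may never happen. That also stands, and the concern is with the rule if it is used.

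A reader might also link this to the C.5 analysis of treatment duration, which uses 6-week KCCQ and Vigor, and suppose that an unblinded person collects them by telephone at week 6. That is conjecture. The same analysis uses echocardiographic and BNP changes, which a call cannot supply. The conflict over 6-week data is real but separate.

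On the powder, no passage describes the taste or odor of the placebo. The sweetness of D-ribose is slight, and the label has the powder mixed in water. The documents do not say that patients know the run-in powder is placebo, so noticing a change need not tell them which product is active. The general promise of matching placebos counts for something. But it names neither taste nor odor, and a cellulose-only composition leaves little room for such a match.

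**Conclusion.** The point holds in limited form and should be fixed. The contradiction about who is blinded, the call restricted to treatment patients, and the missing taste and odor specification are all plain in the text. Whether they cause bias is not known, and the bias may be nil.

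The false-positive figures depend on a shift that has no source in the documents and on there being no drug effect. They should not be read as the error rate this trial will have. They show only that a shift well below the plan's 10-point target could matter at SD 12.3, and that it would matter much less at SD 25.3.

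Two further inferences are not supported. That the Project Director may take consent, and that the cardiologist is unblinded, are not routes to biased KCCQ or Vigor scores. The cardiologist's status matters only for correcting the statement on concealment. Nor do the documents show that any participant will in fact tell the powders apart.

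**What to change.** 1. Reconcile the concealment statement in C.2 with the potential-problems paragraph and monitoring plan 1.2. List who is unblinded and state that they collect no outcomes. Have the Research Associate or other existing blinded staff make the follow-up calls and do any assisted completion of KCCQ and Vigor. The plan does not now say that the Research Associate is blinded, so this must be newly stated.
2. Replace the call for treatment patients only with one adherence-contact rule and script, applied identically in all four arms at the existing calls.
3. For powder not yet made, specify taste and odor matching of the placebo, including the run-in supply, within the allergen limits of Appendix 9. The cellulose-only wording would change with it. Otherwise, state possible unblinding of the three D-ribose-powder comparisons as a limitation.
4. Optionally, add one treatment-guess item at week 12, asked after KCCQ and Vigor and reported by arm. Guesses may reflect perceived benefit and should be read with that caveat.

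Leave the routes for reporting side effects and the staffing of consent as they are. Treat the conflict over 6-week data (C.5 against C.2, C.3 and Human Subjects 1.1) as a separate point to be reconciled.

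The cost is a protocol amendment and moving some of the 828 short calls between existing staff, within a total of under 69 hours. The documents do not give the number of assisted questionnaires. Reformulating the placebo is not assumed to be cheap, so it is asked only for powder not yet made. The sample size does not change.
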